## **2.3 INVESTIGATIONAL PRODUCT**

The drug product is a size '1' white, opaque hydroxypropylmethyl cellulose capsule filled with a solution of CXA-10 (25% or 50% w/w) in medium chain triglyceride oil with 0.05% of butylated hydroxytoluene as an antioxidant. Fumed silica may be added as a thickening agent. Capsules are provided in the dose strength of 75 mg or 150 mg. The filled capsules are packaged in white high-density polyethylene containers (18 capsules per bottle) with child resistant closures.

**Dosages:** The dose for this study is 300 mg once daily (two 150 mg capsules daily)

### **2.3.1. Investigational Product Preparation and Dispensing**

CXA-10 will be obtained from Complexa, Inc. The labeling and packaging will be conducted according to Good Clinical Practice and regulatory requirements. The University of Pittsburgh Medical Center Investigational Drug Services (UPMC-IDS) Pharmacy will be utilized for dispensing of the study drug. The study drug is administered only to subjects enrolled in the study and in accordance with the protocol.

### **2.3.2. Administration of Investigational Product**

CXA-10 will be administered orally. Subjects will be instructed to take their CXA-10 dose once daily in the morning with food. The food can contain up to approximately 30% of calories from fat. A high fat meal must be avoided. A list of recommended meals/snacks will be provided to subjects.

Dosing will begin on Visit 3 (Week 0) in the clinic where subjects will self-administer study medication. Dosing will then commence at home. However, subjects should not take their morning dose of study medication at home when Visits 4, 5, 6, 7 and 8 are scheduled. These doses will be administered in the clinic.

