
**END OF TREATMENT: All end of treatment study procedures will take place over 3 visits and can be completed in any order to accommodate scheduling needs.**

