**Visit 6 (Week 12 ± 5d – End of treatment)**

This visit will take place at UPMC Montefiore. Subjects will be asked to fast a minimum of 12 hours to perform the assessments listed below. The visit will last approximately 6 hours.

- Brief physical exam with a body weight measurement and WHO Functional class assessment
- Vital signs (temperature, blood pressure, respiratory rate, heart rate, and pulse oximetry measurements are taken).
- ECG
- Clinical laboratory tests and urinalysis (fasting glucose, comprehensive metabolic panel, fasting lipid profile, CBC/Diff/Plt, uric acid, PT/INR, hemoglobin A1c (this test is performed if subject has abnormal HbA1c))
- Research blood samples for biomarkers, cytokines measurements, NT-proBNP
- Oral (saliva, tongue scraping) and stool samples for microbiome analysis; subjects may be provided a stool collection kit and return the sample in a pre-paid envelope by USPS mail.
- Urine pregnancy test for female child-bearing potential
- IVGTT
- Health related quality of life questionnaire - Pulmonary Arterial Hypertension-Symptoms and Impact (PAH-SYMPACT®)
- Return accelerometer for data download
- Concomitant medications assessment
- AE assessment

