**Visit 7 (Week 12– End of Treatment)**

Subjects will report to the clinic on the morning of Week 12 after a minimum 8-hour overnight fast. Subjects should not take their study medication that morning, prior to arriving at the clinic for their pre-dose assessment.

- Brief physical exam
- Echocardiogram (may be completed on a separate day if a scheduling conflict occurs)
- RHC. Pulse oximetry and automated blood pressures will be measured at regular intervals.
- Hemodynamic measures such as pulmonary vascular resistance (PVR), mean pulmonary artery pressure (mPAP) and left and right ventricular filling pressures, will be measured at baseline and 30 minutes post drug dose and CXA 10 metabolites will be measured with pharmacokinetics sampling time points at baseline and 4-6 hours post drug dose. Food will be given prior to dosing. Research blood samples for biomarkers, cytokines measurements (samples collected at the same times as PK samples)
- Concomitant medications assessment
- AE assessment

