### **2.2.3 Description of Study Procedures**

Subjects must present to all study visits in the morning. Subjects must fast from all food and drink (except water) for a minimum of 12 hours prior to Visits 2 and 6 (12-hour fast is required for leptin analysis). Subjects must fast from all food and drink (except water) for a minimum of 8 hours prior to visits 1, 4, 5, 7, 9.

During treatment visits (Visits 3 through 9), when at the study site, subjects will have access to breakfast, lunch and dinner if appropriate. Subjects will eat breakfast or a morning snack (containing no more than 30% fat) after completion of all pre-dose assessments and just prior to

the time of dosing. Subjects will be instructed to take their dose of study medication at the clinic at each scheduled office visit (Visits 3, 4, 5, 7, 8). The date and time of dosing will be recorded at these visits.

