### **Efficacy Assessments**

Right Heart Catheterization (RHC): RHC is performed routinely as a clinical standard of care procedure for diagnostic purposes in this population. RHC will be performed at Screening and at the end of the treatment (Visit 6 – Week 12).

Briefly, RHC will be performed with a balloon tipped, flow-directed, pulmonary artery catheter (e.g. 7F Swan Ganz catheter) inserted through a sheath in the internal jugular vein under continuous

ECG monitoring. An alternate vein may be used at the physician's discretion. All measurements will be recorded with the subject in a supine position, at rest, breathing room air or with supplementary oxygen to obtain peripheral saturations above 90%. Hemodynamic recording of right atrial, right ventricular, pulmonary artery pressures, pulmonary artery wedge pressure and cardiac output will be made. Parameters for analysis will include: Mean RAP, RVSP, RVDP, PASP, PADP, Mean PAP, Mean PAWP, Thermodilution Cardiac Output, PVR, Cardiac Index, and Pulmonary Vascular Compliance. Mixed venous oxygen saturation (SvO2) will be determined from a sample drawn from the Swan-Ganz catheter. Other parameters may be obtained as data permit.

**Echocardiogram:** Noninvasive transthoracic echocardiograms will be completed to assess RV function by measures such as tricuspid annular plane systolic excursion (TAPSE) as well as tissue Doppler of the lateral tricuspid valve anulus (S').

**Six Minute Walk Distance Test and Borg Dyspnea Scale:** The 6MWD test will be performed according to a protocol-specific modification of the American Thoracic Society guidelines. The 6MWD test measures the distance an individual is able to walk over a total of six minutes on a hard, flat surface. The Borg Scale is a method of rating perceived exertion during exercise. It should be performed immediately after the 6MWD test.

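### Sections 2.3.2 and 2.2.3 disagree on whether a dose is given on the Visit 6 day, so the time from last dose to the Week 12 PVR reading could depend on visit order

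*Combined protocol and SAP*

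**What the plan says.** On dosing around the end-of-treatment visits, the protocol says the following.

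- Section 2.3.2 (Administration of Investigational Product): "subjects should not take their morning dose of study medication at home when Visits 4, 5, 6, 7 and 8 are scheduled". The next sentence reads "These doses will be administered in the clinic". Taken together, these make Visit 6 a clinic-dosing day.
- Section 2.2.3 (Description of Study Procedures) has subjects dose "at the clinic at each scheduled office visit (Visits 3, 4, 5, 7, 8"). Visit 6 is not in that list. The date and time of dosing are to be recorded at the listed visits.
- Section 2.2.2, Visit 6: "Subjects will be asked to fast a minimum of 12 hours to perform the assessments listed below". The list that follows includes the glucose tolerance test and laboratory work. It has no dosing step and no PK sample. Table 1 (PK/PD sampling windows) has no Visit 6 column. By contrast, the lists for Visits 4, 5 and 8 each tell the subject to take the drug in the clinic.
- Section 2.2.2, note ahead of the end-of-treatment visits: "All end of treatment study procedures will take place over 3 visits and can be completed in any order". No spacing between the visits is stated.
- Section 2.2.2, Visit 7: "Subjects should not take their study medication that morning, prior to arriving at the clinic for their pre-dose assessment". Hemodynamics are read before the dose and again 30 minutes after it.

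On which visit holds the catheterization, Section 2.2.3 (Efficacy Assessments) says "RHC will be performed at Screening and at the end of the treatment (Visit 6 – Week 12"). Section 2.2.1 and the Visit 7 procedures put it at Visit 7.

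**The concern.** Change in PVR at 12 weeks is the primary efficacy measure. The trial is single-arm and compares each subject with their own baseline, so no control group would show up a difference caused by when the Week 12 reading is taken.

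The home-dose instruction and the clinic instructions sit in different sections and disagree about Visit 6. If the disagreement is settled in practice by giving no dose that day, the time from last dose to the pre-dose PVR depends on how the three visits happen to be scheduled. Some subjects would be read after the usual one-day interval and others after two days. Section 2.5.1 frames the PVR power calculation around vasodilatory effects, for which time since dosing could plausibly matter. The Visit 8 pre-dose PK sample is exposed in the same way when Visit 6 is the day before Visit 8.

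The conflict over the RHC visit number is a separate discrepancy. Followed literally, the Efficacy Assessments text would put the catheterization, for which the Visit 7 text plans a post-dose reading, on a visit that Section 2.2.3 does not list for dosing.

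**Working it through.** **1. The plan's own figure.** Section 2.5.1 assumes a PVR decrease of 2.3 Wood units with SD 4.1, two-sided alpha 0.05 and 80% power. Section 2.5.2 specifies a paired t-test. With N = 27 the noncentrality is (2.3 / 4.1) × √27 = 2.915. The noncentral t with 26 degrees of freedom gives power 0.801, and 27 is the smallest N that reaches 0.80. Allowing for 10% drop-out, 27 / 0.90 = 30. The stated 27 and 30 both reproduce, and this point does not dispute them. They matter here only because they leave no spare power.

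**2. The passages side by side.**

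| Source | Home dose on Visit 6 day | Clinic dose at Visit 6 |
|---|---|---|
| Section 2.3.2 | withheld | given |
| Section 2.2.3 list | not addressed | not listed |
| Visit 6 procedures and Table 1 | not addressed | no dosing or PK step |

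**3. Time from last dose to the Visit 7 pre-dose reading**, with once-daily morning dosing (Section 2.3.2).

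- Visit 6 dose given: about 24 h, in every visit order.
- Visit 6 dose not given, and Visit 6 not on the day before Visit 7: about 24 h, because a dose is taken on the intervening day.
- Visit 6 dose not given, and Visit 6 on the day before Visit 7: 24 + 24 = about 48 h.

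**4. Visit orders.** Three visits can be ordered in 6 ways. Visit 6 immediately precedes Visit 7 in 2 of them (6-7-8 and 8-6-7) and immediately precedes Visit 8 in 2 others (6-8-7 and 7-6-8). This counts orders and is not a probability. The visits must also fall on consecutive days, which the protocol neither requires nor rules out.

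**5. What a missed dose would do to the trough.** The documents give no half-life, so the half-lives here are assumptions. The ratio of the 48 h to the 24 h concentration is 2^(−24 / t½).

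| Assumed t½ (h) | 48 h / 24 h ratio |
|---|---|
| 6 | 0.06 |
| 12 | 0.25 |
| 24 | 0.50 |
| 33.6 (168 / 5) | 0.61 |
| 42 (168 / 4) | 0.67 |

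The last two rows take the statement under Visit 3a that steady state is reached by day 7 (168 h) and count it as 5 or 4 half-lives. These are plasma ratios and cannot be turned into PVR.

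**6. Illustration of power.** Suppose a share f of subjects is read at 48 h and keeps a fraction r of the effect. The mean becomes 2.3 × [1 − f(1 − r)] and the SD becomes √{4.1² + f(1 − f)[2.3(1 − r)]²}. With f = 0.25, an arbitrary value:

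| r | Mean | SD | Power at N = 27 |
|---|---|---|---|
| 1.00 | 2.30 | 4.10 | 0.80 |
| 0.75 | 2.16 | 4.11 | 0.75 |
| 0.50 | 2.01 | 4.13 | 0.68 |
| 0 | 1.72 | 4.22 | 0.53 |

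Neither f nor r can be taken from the documents. The table shows only that the answer runs from no loss to a material one.

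**The case against.** The strongest reply is that no passage tells anyone to omit the Visit 6 dose. Section 2.3.2 withholds the home dose and at once provides for a clinic dose. The Section 2.2.3 list omits Visit 6 but does not forbid dosing there, and its lead-in covers every scheduled office visit, which Visit 6 is. The Visit 6 procedures are merely silent. A reader might infer that the protocol orders a skipped dose, and the documents do not support that. This part of the reply stands: the defect is a contradiction that leaves room for a missed dose.

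The 48 h interval also needs several things together: the site resolves the conflict by omitting the dose, Visit 6 is the calendar day before Visit 7, and the analysed value is the pre-dose one. That stands too, with one qualification on the last condition. Section 2.2.1 and the Appendix A footnote limit the acute-response evaluation to the first 10 subjects. On that reading, about 27 − 10 = 17 completers would have only a pre-dose value. Section 2.4 does not say which reading is the endpoint.

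If the RHC were held at Visit 6, as the Efficacy Assessments text says, a dose omitted that day could not lengthen the interval before it. That is correct, and it is why the visit-number conflict is a separate item. Biomarkers drawn fasting at Visit 6 are likewise unaffected by a dose omitted later that day.

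Finally, much of the dose timing is already captured. Subjects record the date and time of dosing at home (Section 2.2.1), sites record it at the listed dosing visits (Section 2.2.3), and the note to Table 1 requires the dosing time before each PK sample. This stands, so a new data field would add little. It does not make the interval uniform.

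**Conclusion.** The point holds as a contradiction in operative dosing text. Sections 2.3.2 and 2.2.3 and the Visit 6 procedures do not agree on the Visit 6 dose, and the Efficacy Assessments text disagrees with Section 2.2.1 and the Visit 7 procedures on where the Week 12 catheterization takes place. Confidence in this is high.

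The consequence is conditional. If a site gives no dose on the Visit 6 day and that day immediately precedes Visit 7, the pre-dose PVR is read at about 48 h instead of about 24 h. Otherwise it is read at about 24 h. The Visit 8 pre-dose PK sample is affected only if Visit 6 is the day before Visit 8.

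A reader might go further and conclude that the Week 12 PVR effect is diluted. The documents do not support that. They give no half-life and no time course for loss of a PVR effect, and the rationale is largely about disease modification, under which one late reading might change nothing. Added variability or dilution is possible, its size cannot be established, and it could be nil. The sample size of 27 is not in question. The correction is worth making because it is cheap and the single-arm comparison has no other protection against a scheduling artefact.

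**What to change.** 1. Reconcile Section 2.3.2, the dosing list in Section 2.2.3 and the Visit 6 procedures so that all three say the same about the Visit 6 dose. Which rule to keep is for the sponsor.
2. Reconcile the RHC visit number in Efficacy Assessments with Section 2.2.1 and the Visit 7 procedures.
3. Under whichever rule is kept, make the interval from last dose to the Week 12 RHC the same for every subject. The end-of-treatment note now says the procedures "can be completed in any order to accommodate scheduling needs", and it would need a matching qualification.
4. Report the Week 12 PVR together with that interval, derived from the dose times already collected under Sections 2.2.1 and 2.2.3 and the note to Table 1.

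The cost is wording changes in a few places and slightly less freedom in scheduling the three end-of-treatment visits. Sample size and the planned test do not change.

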### **2.3.3. Dose Selection**

The doses of CXA-10 for this study is 300 mg once daily (with food containing up to approximately 30% fat). The highest repetitive dose administered in the Phase I, CXA-10-202 study was 450 mg for 14 days in a fasted state. Analysis of preclinical exposure response data predicted the human therapeutic dose at approximately 150 mg daily. Subsequently, more data has been developed including data from the Phase 1 Multiple ascending dose (MAD) study and the Phase 2 FSGS Study (clinicaltrials.gov NCT02460146 and NCT03422510, respectively). The MAD data was used to select doses of 75, 150 and 300 mg QD for the FSGS study which is approved by the FDA and is currently ongoing. An interim look by Complexa at the first 21 subjects who completed 90 days of dosing in FSGS study suggests that the higher dose (300 mg/day) may be more effective and no drug-related SAEs have been reported.

In this study, dosing will take place in the fed state (food with up to approximately 30% fat). This regimen has been shown to improve GI tolerability without impacting PK. In Study CXA-10-202, healthy, obese, male subjects received CXA-10 once daily for 14 days in the fasting state. Under the fasted dosing condition, mild to moderate, intermittent diarrhea of probable to definite causality was reported by 5 of 10 subjects (50%) at the 150 mg dose and by 9 of 10 subjects (90%) at the 450 mg dose. Subjects at the 450 mg dose level also received one CXA-10 dose with a high fat meal (50% fat) and the incidence of diarrhea decreased (3 of 10 subjects [30%]). While the high fat meal (50% fat) resulted in a lower incidence of diarrhea, CXA-10 exposure was increased compared with the fasting state (Cmax and AUC increased by 2.2-fold and 1.6-fold, respectively, after a high fat breakfast). In Study CXA-10-203, a 150 mg dose of CXA-10 was administered to healthy, male subjects once daily on Days 4 to 12 of the study in the fed state (after a standard breakfast of approximately 30% fat). When CXA-10 was administered with a standard breakfast (30% fat), only 1 of 10 subjects (10%) experienced diarrhea. This subject's diarrhea was considered unlikely to be related to CXA-10 and was instead attributed to a Norovirus infection. CXA-10 PK after dosing with a meal of approximately 30% fat was similar to the PK after dosing in the fasting state.

### **2.3.4. Overdose**

There is currently no information available on the medication effects of an overdose of oral CXA-10, although a single dose of 1200 mg and a total daily dose of 1800 mg (900 mg twice within 6 hours) was administered with the most notable effect of Grade 1 to Grade 2 diarrhea.

If an overdose is suspected, the subject should be maintained under close medical observation and be intensively monitored for potential GI and cardiovascular events. Diarrhea has been the most obvious and consistent side effect thus far seen, and an overdose could possibly result in profound and persistent diarrhea. Subjects may experience vasovagal signs and symptoms, dehydration and electrolyte abnormalities should such an event occur due to an overdose. Medical intervention and subsequent care should be instituted as appropriate to the signs and symptoms of any AE.

### **2.3.5. Treatment Period**

Twelve weeks.

### **2.3.6. Investigational Product Storage and Accountability**

Study drugs used during the trial will be stored at the UPMC-IDS in accordance with Good Clinical Practice (GCP) in a place accessible only to authorized personnel. CXA-10 capsules should be stored refrigerated between 2 and 8°C (35 to 46°F). Brief excursions (for up to 48 hours) are permitted at room temperature (20 to 25°C [68 to 77°F]). Storage in direct sunlight or at temperatures greater than 25°C (77°F) should be avoided.

Adequate accountability records of study drug received, dispensed, used will be maintained throughout the course of the study. The study investigators or the study coordinator will document the amount of study drug dispensed from UPMC-IDS. The study drug accountability records will be maintained at UPMC-IDS throughout the course of the clinical trial.

### **2.3.7 Concomitant Medications**

Concomitant medication assessments will be conducted throughout the study. While it is expected that subjects' medication regimens remain stable over the course of the study, changes are permitted if medically indicated. Subjects will be asked if they have had any change(s) to their medication regimen since their last visit, except for visit 3a. Any medication regimen changes will be documented in the Concomitant Medication section of the CRF.

#### **Permitted Medications**

Any concomitant medication to treat adverse events will be recorded in the Concomitant Medication section of the CRF. All subjects are required to take their stable regimen of PAH therapy during the study, and no regimen changes will be permitted during the study (unless indicated for safety).

#### **Precautionary and Prohibited Medications**

During the study, subjects are not allowed to take the following medications:

- Intravenous inotropes (e.g. dopamine, dobutamine)
- Long or short acting nitrates
- Newly prescribed drug or increased dose of an existing drug that is known to prolong QTc interval or has been associated with Torsades de Pointes. Stable doses of these drugs are permitted (i.e., subject has received the same dose and regimen for at least 30 days prior to Screening (Visit 1) with no anticipated changes to the dose or regimen during the course of the study).
- Herbals, natural medications and fish oil
- Drugs that may affect the measurement of serum creatinine (e.g. cimetidine, Bactrim, Pyridium).
- Dimethyl fumarate (Tecfidera™)
- Simvastatin at doses greater than 20 mg (Zocor), Vytorin, or any other combination therapy containing simvastatin at doses greater than 20 mg.
- Any other investigational drug regardless of route (topical, intranasal, etc.).

## **2.4 STUDY ENDPOINTS**

Primary Endpoint:

The primary endpoint measures the incidences of treatment-emergent adverse events.

Secondary Endpoints:

The primary efficacy endpoint measures the change from baseline in Pulmonary Vascular Resistance (PVR) assessed by Right Heart Catheterization at 12 weeks.

Other secondary endpoints measure:

- Change from baseline in hemodynamic parameters including Cardiac Output (CO), Cardiac index (CI), mean Pulmonary Artery Pressure (mPAP), Pulmonary Artery Wedge Pressure (PAWP), Mean Right Atrial Pressure (mRAP), and compliance (SV/ (sPAP-dPAP) at 12 weeks
- Change from baseline in RV function including tricuspid annular plane systolic excursion (TAPSE) and tissue Doppler of the lateral tricuspid valve anulus (S') as assessed by echocardiograms at 12 weeks
- Change from baseline in functional exercise capacity by assessing 6 minute walk distance test with Modified Borg Dyspnea Scale at 12 weeks
- Change from baseline in the levels of serum NT-proBNP at 12 weeks
- Change from baseline in WHO Functional Class at 12 weeks
- Change from baseline in patient reported outcomes measured by PAH-SYMPACT® questionnaire at 12 weeks
- Change from baseline in daily physical activity assessed by personalized activity monitor at 12 weeks
- Pharmacokinetic endpoint: CXA-10 parent and metabolites

Exploratory Endpoints:

- Change in insulin sensitivity by intravenous glucose tolerance test at 12 weeks
- Pharmacodynamic endpoint: change from baseline in serum biomarkers, leptin, inflammatory cytokines (IL-17, IL-6, TNF $\alpha$ , MCP-1) and hsCRP at 12 weeks
- Pharmacokinetic - Pharmacodynamic relationship of CXA-10 on relevant efficacy, safety and biomarkers endpoints, if the data allow
- Epidemiological relationships of oral and gut microbiome and PAH

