**Visit 8 (Week 12 – End of treatment)**

This visit will take place at UPMC Montefiore and the visit will last up to about 7 hours. The subject does not need to fast.

- 6MWT
- Blood draw for Population PK sampling (pre-dose and 4-6 hours after taking the study drug) Subjects will be instructed to take the study medication at the clinic after a breakfast/morning snack containing up to approximately 30% fat
- Research blood samples for biomarkers, cytokines measurements (samples collected at the same times as PK samples)
- Concomitant medications assessment
- AE assessment
- Dispense 1st month of open label CXA-10 after the completion of all end of treatment testing (optional)

Following the completion of all end of treatment assessments, patients have the option to discontinue treatment and have a safety follow up at Visit 9 or patients may also choose to enter the open label extension for 6 months. If patients are in the open label extension, Visit 9 will be the month 1 follow up. If patients wish to enter the open label extension, the first month supply will be dispensed at the end of their final visit for end of treatment testing.

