## 2.5 STATISTICAL ANALYSIS

### 2.5.1 Sample Size Determination

We plan to enroll 30 subjects with PAH, allowing for a conservative drop-out rate of 10%, in this open label trial of oral CXA-10. We expect to see decrease in the PVR after 12 weeks of therapy. The intention to treat (ITT) population will consist of all subjects who have received at least one dose of study medication. To estimate our effect size for power calculations, we use data from the SUPER-1 sildenafil PAH trial (a randomized placebo control trial evaluating the effects of 20 mg, 40 mg or 80 mg TID of sildenafil in subjects with PH). Using the hemodynamic data from the 80 mg arm of the SUPER-1 trial and making a conservative assumption that our therapy will only have an effect that is 70% of sildenafil (decrease in PVR of 2.3 woods units with SD of 4.1), the sample size required for 80% power and P = 0.05 is 27 subjects (Table 2). We anticipate more than sufficient power to detect vasodilatory effects of NO2-OA administration (decreased PVR) after 3 months of therapy. Based on our extensive phase 1 data with CXA-10 formulations, we

anticipate the drug will cause no systemic blood pressure changes and no increases in methemoglobin levels.

**Table 2 Required sample size for different effect,  
Power =0.8 ,  $\alpha=0.05$ , two sided test**

% of Sildenafil	Mean (SD) PVR change, Woods unit	N
90	3.0 (4.9)	23
80	2.6 (4.2)	23
70	2.3 (4.1)	27

With safety as the primary outcome measure, we use Fleming's single stage phase II design with the following assumptions:  $\alpha = 0.05$ , Power= 0.80, lower proportion for rejection 70% (with no SAEs), higher proportion of acceptance 90% (with no SAEs) with maximum recruited patients of 27 patients resulting in a minimum number of success (with no SAEs to indicate that the treatment is safe) is 24. Thirty patients will be enrolled to compensate for up to 10% lost-to follow-up.

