## 2.5.2 Statistical Analysis

Change of each outcome from baseline will be presented by median (IQR). Primary analysis will be performed by paired t-test comparing continuous outcome in 12-weeks vs. baseline. All data will be tested for normality, and non-normal data will be tested by Wilcoxon signed rank test. We will also use mixed effect models with restricted maximum likelihood estimation to test the change of outcome during the 12 weeks of intervention.

Demographics and baseline characteristics will be listed and summarized descriptively. Safety will be evaluated via the incidence of AE's, changes in clinical labs, and vital signs. AEs will be coded by system organ class and preferred term according to the most recent edition CTCAE. AEs will be summarized by frequency, severity, and relationship to study medication. Clinical labs will be compared to normal ranges and flagged if found to be of clinical concern. Results will be presented as observed changes and depicting changes from baseline to defined study timepoints.

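### The declared primary endpoint (adverse event incidence) has no decision criterion, and the only safety rule (24 of 27 subjects SAE-free) has no listed endpoint, population, window or analysis

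*Combined protocol and SAP*

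**What the plan says.** The synopsis and section 2.4 use the same sentence: "The primary endpoint measures the incidences of treatment-emergent adverse events". Neither gives a counting unit, a time window or a threshold. Section 2.4 places the change in PVR under the secondary endpoints and calls it the primary efficacy endpoint.

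Section 2.5.1 sizes the trial twice. One calculation uses the change in PVR. The other concerns safety: "With safety as the primary outcome measure, we use Fleming's single stage phase II design". Its variable is the proportion of subjects with no SAE, 70% against 90%, with alpha 0.05, power 0.80 and 27 patients, and its rule is that the "minimum number of success (with no SAEs to indicate that the treatment is safe) is 24". The same section defines the intention-to-treat population as everyone who took at least one dose, and plans to enrol 30.

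Section 2.5.2 states: "Primary analysis will be performed by paired t-test comparing continuous outcome in 12-weeks vs. baseline". Safety is then described through adverse event incidence, laboratory values and vital signs, with events summarised by frequency, severity and relationship to drug.

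Four other places bear on the point. The table in section 3.4.1 refers to hemodynamics as a primary endpoint. Section 6.4.5 limits SAEs to events thought to be related to the study. Section 6.4.8 says removed subjects are replaced. Under Visit 8, after the end-of-treatment assessments, "patients may also choose to enter the open label extension for 6 months", in which case Visit 9 (Week 16) becomes their month 1 extension visit.

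**The concern.** Endpoint, decision rule and primary analysis should describe one variable. Here they describe three: adverse event incidence, SAE-free subjects, and week-12 change in a continuous measure.

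A team following sections 2.4 and 2.5.2 would report an adverse event incidence with nothing to judge it against, and could present PVR as the primary result because it carries the label of primary analysis. A team following section 2.5.1 would declare the treatment safe or not, but would first have to decide who is in the denominator, how long SAEs are counted, and whether an unrelated SAE counts. In a single-arm, open-label trial these choices should be fixed before the data are seen.

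**Working it through.** **Step 1. The places side by side.**

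| Place | Variable | Criterion | Analysis |
|---|---|---|---|
| Synopsis, 2.4 | Incidence of treatment-emergent adverse events | None | Descriptive summary in 2.5.2 |
| 2.5.1, safety | Subjects with no SAE | At least 24 of 27 | None in 2.5.2 |
| 2.5.1, Table 2 | Change in PVR | 80% power, two-sided 0.05 | Paired t-test in 2.5.2 |
| 2.5.2 | Continuous outcomes, Week 12 vs baseline | None stated | Paired t-test, called primary |

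Only the PVR row is complete from sizing to analysis. The two safety rows each lack what the other has.

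**Step 2. The PVR sizing reproduces.** With mean change 2.3, SD 4.1 and a two-sided paired t-test (noncentral t), n = 27 gives power 0.801. Dropout: 27/0.9 = 30.

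**Step 3. The Fleming figures reproduce, except for power.** The sidedness of alpha is not stated. I take it as one-sided, which is usual for this design.

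- Normal approximation: n = [(1.645·√(0.7·0.3) + 0.842·√(0.9·0.1))/0.2]² = 25.3, so 26. The smallest exact design is 28 subjects with cut-off 24. The plan's 27 lies between.
- Exact type I error at n = 27: P(X ≥ 24 | 0.70) = 0.0151 + 0.0042 + 0.0008 + 0.0001 = 0.020. A cut-off of 23 gives 0.059. So 24 is the correct cut-off.
- Exact power at n = 27: P(X ≥ 24 | 0.90) = 0.2333 + 0.2520 + 0.1744 + 0.0581 = 0.718, against the stated 0.80.

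**Step 4. The cut-off depends on the denominator.** The rule is written for 27, but the intention-to-treat definition takes in all dosed subjects, about 30 before any replacements. Exact binomial results:

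| Dosed | Cut-off | Type I error (70%) | Power (90%) |
|---|---|---|---|
| 27 | 24 | 0.020 | 0.718 |
| 28 | 24 | 0.047 | 0.858 |
| 29 | 24 | 0.093 | 0.936 |
| 29 | 25 | 0.038 | 0.842 |
| 30 | 24 | 0.160 | 0.974 |
| 30 | 26 | 0.030 | 0.825 |

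Keeping 24 while the denominator grows to 29 or 30 breaks the 0.05 limit.

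**Step 5. The result depends on the window.** The documents give no SAE rate for this population, so I assume a 12-week risk at constant hazard, with all 27 followed. The SAE-free proportion at week w is (1 − risk)^(w/12). For a 10% risk at Week 16 it is 0.9^(16/12) = 0.869.

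| Assumed 12-week SAE risk | P(≥ 24 of 27), Week 12 | P(≥ 24 of 27), Week 16 |
|---|---|---|
| 5% | 96% | 90% |
| 10% | 72% | 52% |
| 15% | 41% | 20% |

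**Step 6. The SAE definition is not settled.** Section 6.4.5 makes relatedness part of the definition, while section 6.4.2 provides for an SAE found to be clearly unrelated. Who counts as SAE-free depends on which use applies.

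**The case against.** The plan can be defended on several points, and most of them stand as limits on the concern.

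- The t-test sentence is confined to continuous outcomes, and section 2.5.2 treats safety separately. A reader might infer that the plan applies a t-test to adverse events. It does not, and the declared endpoint does have a descriptive analysis.
- A reader might infer that the safety verdict flips according to the section followed. That would need two competing rules, and there is one rule against none. Nor does any section apply 24 of 27 to subjects free of any adverse event, so a pass probability on that basis tests a reading the plan does not contain.
- A reader might infer that the trial is sized on SAE-free subjects alone. Table 2 reaches 27 from PVR independently.
- A reader might count SAEs through the 6-month extension. The objective, Aim 1 and the treatment period are all tied to 12 weeks, and the extension is optional and begins after end-of-treatment testing. Only Week 12 against Week 16 is a fair ambiguity.
- Section 2.4 lists PVR as secondary, which lowers the risk of its being promoted, although sections 2.5.2 and 3.4.1 pull the other way.
- Replacing the endpoint is not the only remedy. Keeping adverse event incidence as a descriptive primary endpoint, with the SAE-free rule named as the decision criterion beside it, would also reconcile the text.

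None of this supplies a criterion for the declared endpoint, or an analysis, population and window for the rule.

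**Conclusion.** The concern holds as an inconsistency between the endpoint, sizing and analysis sections. The declared primary endpoint has no decision criterion. The one safety criterion rests on a variable that is not a listed endpoint and is never carried into the analysis section. The label of primary analysis sits on tests of continuous outcomes.

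The size of the problem lies in what is left open. The exact type I error ranges from 0.020 (24 of 27) to 0.16 (24 of 30) according to who is counted. Exact power at 24 of 27 is 0.718 rather than 0.80. The chance of meeting the rule moves from 72% to 52% between a Week 12 and a Week 16 window.

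The type I error and power figures rest on exact binomial calculation at the plan's own 70% and 90%, with one-sided alpha assumed. The window figures rest on an assumed 10% 12-week risk, constant hazard and full follow-up of 27 subjects. They show sensitivity and do not predict the result.

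**What to change.** - **Synopsis and 2.4.** Name the proportion of subjects with no SAE as the primary safety endpoint, or as the stated decision criterion alongside descriptive adverse event incidence. Start the window at first dose, exclude events after any extension dose, and state whether it ends at Week 12 or includes the 4-week follow-up. If it runs to Week 16, extension entrants stop contributing at their first extension dose, so follow-up will be unequal and the text should say how that is handled.
- **SAE definition.** State whether SAEs count regardless of relatedness, and reconcile sections 6.4.2 and 6.4.5.
- **2.5.2.** Make the primary analysis an exact one-sided binomial test against 70%, with an exact confidence interval, in all dosed subjects. Keep subjects who are later replaced in the denominator. Give the cut-off for each possible denominator (24 of 28, 25 of 29, 26 of 30), and report that 24 of 27 has exact power 0.718.
- **Labels.** Call the paired PVR test the primary efficacy (secondary) analysis, correct the wording in section 3.4.1, and keep adverse event incidence as a descriptive summary.

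The cost is amendment wording in the synopsis and sections 2.4, 2.5.1, 2.5.2, 3.4.1 and the SAE definition. Planned enrolment of 30 and data collection do not change: 26 of 30 meets both the 0.05 limit and 80% power.
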